Subjects leaving the trial for any reason between two clinic visits, or between the first phone contact and the succeeding clinic visit, will not have a compliance measurement for the time between the last clinic visit (or Visit 4) and trial exit. For these subjects, an assumption on how long C_{LCV} (or C_{V4}) is assumed valid must be made. Denote the last date for which C_{LCV} (or C_{V4}) is assumed valid $D_{LCV/V4}$. For subjects experiencing recurrence, death, or other cancer, $D_{LCV/V4}$ will be defined as the date of last IMP intake, if such a date is registered in the eCRF, or the event date (see Section 6.2.1 for definition), whichever comes first. For subjects leaving the trial before an endpoint or before trial completion, $D_{LCV/V4}$ will be defined as the date of last IMP intake, if such a date is registered in the eCRF, or the Visit 15 date/EoS date, whichever comes first. For subjects completing 3 years in the trial, $D_{LCV/V4}$ will be defined as the date of Visit 15 (the 3-year follow-up clinic visit). The number of days for which C_{LCV} (or C_{V4}) will be assumed valid will be calculated as days from randomization until $D_{LCV/V4}$, subtracting the number of days on treatment breaks (before $D_{LCV/V4}$) not allowed by the protocol (see above), for each randomized subject having received the IMP at least once.

For subjects reaching a trial endpoint, days from $D_{LCV/V4}$ until the event date will be defined as having 0 % compliance. Similarly, for subjects leaving the trial before completion, days from $D_{LCV/V4}$ until 3 years from randomization will be defined as having 0 % compliance. For all subjects, regardless of trial completion or exit, days on treatment breaks (before $D_{LCV/V4}$) not allowed by the study protocol will be defined as having 0 % compliance. Overall compliance (OC) will be calculated as a weighted average between C_{LCV} (or C_{V4}) and 0, as follows

OC % =
$$\frac{\text{Valid days*C}_{\text{LCV or V4}} + \text{Zero-compliance days*0}}{\text{Valid days+Zero-compliance days}}.$$

Subjects with an EoS event before the first phone contact will not have answered the question on frequency in taking the IMP, or have any pill counts in the eCRF, hence, it is not possible to calculate compliance for such subjects.

See 6.2.2 for derivation of the variables needed for compliance calculation.

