5.2.2 Per protocol populations

The per protocol population at 3 years (PP3) consists of all subjects in the FAP who had at least 80 % compliance, fulfill all eligibility criteria, no significant protocol violations, and have either reached a study endpoint (recurrence, other cancer, or death) within 3 years, or completed at least 3 years in the trial.

The per protocol population at 5 years (PP5) consists of all subjects in the FAP who had at least 80 % compliance, no significant protocol violations, fulfill all eligibility criteria, and have either reached a study endpoint (recurrence, other cancer, or death) within 5 years, or completed at least 5 years in the trial.

Subjects who are thought to fulfil all eligibility criteria at randomization, but later are found not to fulfil all eligibility criteria will be excluded from the PP3 and PP5, for example subjects where Lynch syndrome is discovered after randomization.

Significant protocol violations include more than 12 weeks from surgery until randomization, leaving the study because of pregnancy, lack of compliance with the study protocol, wanting to leave the study, refusal to cooperate, other medical reasons, e.g. initiating another treatment not compatible with ASA, or leaving the trial because of an SAE/AE.

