6.2 Derived variables

6.2.1 Endpoint variables

For the primary endpoint TTR assessed at 3 years, subjects will be censored at the date for which they are last known to be free of CRC recurrence. Subjects who are alive and free of CRC recurrence at 3 years plus 21 days (allowing for the 21-day visit-window) will be censored at that time-point. Subjects who have withdrawn their written informed consent during the trial will be censored at the withdrawal date. Subjects who have relocated, and where information on endpoints is not collectable, will be censored at date of relocation. Subjects who have died will be censored at the date of death. For subjects experiencing CRC recurrence, TTR will be calculated as the number of days from randomization until date of CT/MRI, or EoS date if the aforementioned date is missing, or recurrence date collected separately from sites if recurrence has not been entered into the eCRF (see Section 4.9 for details on data collection). For subjects not experiencing CRC recurrence, TTR will be calculated as the number of days from randomization until date of censoring (see above). The TTR event indicator will be defined as 1 for subjects who have experienced CRC recurrence with a CT/MRI/EoS/recurrence date within 3 years plus 21 days from randomization, and 0 for those that have not. The time variable will be named ttr3y, and the event indicator will be named rec status 3y.

TTR will also be assessed at 5 years (see Section 8.3). The variables *ttr5y* and *rec_status_5y* will be created similarly as described above, with censoring at 5 years plus 30 days.

For the secondary endpoint DFS assessed at 3 years, subjects who are free of CRC recurrence, second primary CRC, other cancer, or death from any cause will be censored at the date for which they are last known to be free of such events. Subjects who are free of the above events at 3 years plus 21 days (allowing for the 21-day visit-window) will be censored at that time-point. DFS will be calculated as the number of days from randomization until recurrence date (see definition in the above paragraph), EoS date, death date or date of other cancer collected separately from sites (see Section 4.9), or the date of censoring (see above). The DFS event indicator will be defined as 1 for subjects who have a DFS event within 3 years plus 21 days from randomization, where DFS events are defined as:

- Having EoS reasons CRC recurrence or death, or

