6.2.2 Variables for compliance calculation

See Section 4.8.2 for the definition of overall compliance.

The number of treatment days until the last clinic visit will be calculated as days from the date of randomization (*A_randomiseringsdatum*) until the date of the last clinic visit (*V_Visitdatum* for the latest clinic visit, where clinic visits are *V_Visit* V5, V6, V7, V8, V9, V10, V11, V13, V15).

The number of dispensed pills at a certain clinic visit will be calculated as 100 times the number of unique package numbers (*S_Package_Number*) for packages that are not shredded (*R2465T32612_MAKULERAD*) or not found at the clinic (*S_Not_Found*).

The total number of dispensed pills will be calculated as the sum of the dispensed pills at each visit.

The total number of remaining pills will be calculated as the sum of the number of remaining pills for each clinic visit (S_returned_number). If the package was lost by the subject (S_Lost_Drug="True"), and S_returned_number equals 0 or "NA", the number of remaining pills for that package will be defined as 100, to not overestimate compliance.

The number of days on break will be calculated as the sum of days from $V_UppehallFromDatum$ until $V_UppehallTomDatum$, for all visits where $V_Uppehall=1$. Treatment breaks that are longer than 30 days and unrelated to adjuvant chemotherapy will be defined as non-compliant with the study protocol. Similarly, breaks that are at most 30 days of related to chemotherapy will be defined as compliant with the study protocol. Days on treatment break that are overlapping with a later registered treatment break will be subtracted.

Compliance for subjects with an EoS event after the first phone contact but before the first clinic visit will be based on the variable *V_LMIntag* for *V_Visit*=V4.

The date for which C_{LCV} (or C_{V4}) is considered valid until ($D_{LCV/V4}$) is $E_sistaintag$, dfs_event_date , $E_endofstudydtm$, or $v15_visitdatum$. The number of valid days will be calculated as the number of days from randomization ($A_randomiseringsdatum$) until $D_{LCV/V4}$, subtracting the number of days on non-allowed treatment break (see above). The number of zero-compliance days will be calculated as days from $D_{LCV/V4}$ until $E_endofstudydtm$ or 3 years from randomization, adding the number of days on non-allowed treatment break.

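### SAP 6.2.2 ends zero-compliance days at study exit or 3 years, where SAP 4.8.2 ends them at the event date; read literally, it can misclassify subjects with an event for PP3 and PP5

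*SAP*

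**What the plan says.** SAP 4.8.2 defines overall compliance as a weighted average of measured compliance, over the days for which it is taken as valid, and zero, over the zero-compliance days. The valid period ends at a date called D_LCV/V4. For subjects with recurrence, death or other cancer, this date "will be defined as the date of last IMP intake, if such a date is registered in the eCRF, or the event date", whichever is earlier. Zero-compliance days then run as follows:

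- Subjects reaching an endpoint: days from D_LCV/V4 "until the event date will be defined as having 0 % compliance".
- Subjects leaving before completion: days from D_LCV/V4 "until 3 years from randomization will be defined as having 0 % compliance".
- All subjects: days on breaks that the protocol does not allow are added.

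SAP 6.2.2 opens with "See Section 4.8.2 for the definition of overall compliance" and then derives the variables. There, "The number of zero-compliance days will be calculated as days from" D_LCV/V4 until E_endofstudydtm or 3 years from randomization, plus days on non-allowed breaks. The event date is not offered as an end date, and the two dates that are offered are not assigned to groups of subjects. The same paragraph lists dfs_event_date and E_endofstudydtm as separate variables among the possible values of D_LCV/V4.

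SAP 6.2.1 dates a recurrence by counting days "until date of CT/MRI, or EoS date if the aforementioned date is missing", or by a site-collected date if the recurrence is not in the eCRF.

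SAP 5.2.2 limits PP3 and PP5 to subjects "who had at least 80 % compliance" who also meet the other conditions. It explicitly keeps subjects who reached an endpoint within the period.

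**The concern.** The definition and the derivation of one variable give different end dates for subjects with an event. Take a subject whose D_LCV/V4 is the event date. Under 4.8.2 no zero-compliance days follow. Under 6.2.2, taken literally, the days from the event to study exit count as zero compliance, although they come after the outcome and after treatment should have stopped.

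The resulting indicator, overall_compl_80, decides membership of PP3 and PP5. Exclusion by this route depends on the outcome, because only a subject with an event can have post-event days counted. It weighs most on early events, where few valid days offset the gap. Event counts are small: the planning inputs in SAP 4.5.2 imply about 150 × 0.18 = 27 placebo recurrences and 150 × 0.18 × 0.38 = 10.3 ASA recurrences in Mutation A, before drop-out. A few misclassified events would therefore be noticeable in PP3. The second statistician who reviews the code under SAP section 9 also could not tell which of the two sections it should match.

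**Working it through.** The plan gives no figure on this point, so there is none to reproduce. The check applies the SAP's own formula under each rule.

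**Inputs**

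- Overall compliance (SAP 4.8.2): OC = V × C / (V + Z), with V the valid days, C the measured compliance in per cent and Z the zero-compliance days.
- Threshold (SAP 5.2.2): OC of at least 80 %.
- C_V4 (SAP 4.8.2): set to 80 % for subjects whose EoS falls after the first phone contact but before the first clinic visit and who report good adherence.
- Gap g from event date to EoS date: **assumed**, since the documents do not give it.
- Simplifications: IMP taken up to the event and no non-allowed breaks, so V is the event day. Three years is taken as 1,096 days.

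**Rule of 4.8.2.** Z = 0, so OC = C. A subject with an event and C of at least 80 % passes.

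**Rule of 6.2.2 with the EoS date.** Z = g, and OC ≥ 80 requires g ≤ V × (C/80 − 1). In whole days:

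| Event day | C = 85 % | C = 90 % | C = 95 % |
|---|---|---|---|
| 182 | 182 × 0.0625 = 11.4, so 11 | 182 × 0.125 = 22.75, so 22 | 182 × 0.1875 = 34.1, so 34 |
| 365 | 365 × 0.0625 = 22.8, so 22 | 365 × 0.125 = 45.6, so 45 | 365 × 0.1875 = 68.4, so 68 |

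Check at day 182 with C = 90 %: g = 22 gives 182 × 90 / 204 = 80.3 %, and g = 23 gives 182 × 90 / 205 = 79.9 %. The tolerance grows with time and adherence. At day 365 with C = 100 %, and at day 730 with C = 90 %, it is 91 days.

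**Compliance fixed at Visit 4.** With C_V4 = 80 % there is no slack. For an event at day 120, a one-day gap gives 120 × 80 / 121 = 79.3 %, and the subject fails.

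**Last intake before the event.** With last intake at day 350, event at day 365, EoS at day 395 and C = 85 %, 4.8.2 gives 350 × 85 / 365 = 81.5 % and 6.2.2 gives 350 × 85 / 395 = 75.3 %.

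**Rule of 6.2.2 with the 3-year end date.** If this branch were applied to a subject with an event at day 365 and C = 100 %, OC = 365 × 100 / 1,096 = 33.3 %. Every event before about day 877 (0.8 × 1,096 = 876.8) would fail even at full compliance.

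**Opposite direction.** Suppose last intake and EoS are both at day 400, a site-collected event is at day 700, and C = 95 %. Then 4.8.2 gives 400 × 95 / 700 = 54.3 %, and 6.2.2 with the EoS date gives 95.0 %.

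**The case against.** Section 6.2.2 points to 4.8.2 for the definition, so its wording can be read as loose shorthand. A programmer who defers to 4.8.2 loses no event. That is a fair reading, but it does not settle the matter. The derivation names the variables to use, leaves out the event date, and lists dfs_event_date one sentence earlier. Code that followed it literally would be wrong by 4.8.2.

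A reader might infer that 6.2.2 does remove events from PP3, because study exit is recorded weeks after the scan. The documents do not support that. They nowhere describe E_endofstudydtm as the date on which a form was completed. SAP 4.8 has subjects leave the IMP part of the trial when an EoS reason is met, and recurrence is such a reason, which is compatible with a gap of zero or a few days. Under 6.2.1 the EoS date is itself the recurrence date when the CT/MRI date is missing, and it can be the event date for a death or another cancer recorded as the EoS reason. In those cases the two rules give the same answer.

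Nor does the effect run only one way, as the last example shows. Many subjects of that kind would be excluded from PP3 anyway, since 5.2.2 counts most reasons for leaving early as significant protocol violations.

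Finally, the stakes are limited. The primary analysis and secondary endpoints 1–5 use the FAP. PP3 and PP5 appear only among exploratory analyses, which are optional and reported without p-values, and the SAP already requires the limits of the per-protocol approach to be highlighted. Membership is assigned before unblinding, so the wording cannot be exploited by arm.

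**Conclusion.** The contradiction stands: for subjects with an event, 4.8.2 and 6.2.2 give different end dates, and 6.2.2 does not say who gets which of its two. Read literally, 6.2.2 can exclude adherent subjects with early events from PP3 and PP5. That requires an EoS date later than the event date by more than V × (C/80 − 1) days, which means 11 to 68 days across the table and a single day where compliance is fixed at 80 %. The gap is an assumption, so the number of subjects affected cannot be derived, and the net direction cannot be stated. The large loss under the 3-year end date arises only if that branch is applied to subjects with events, which 6.2.2 neither says nor rules out. The FAP analyses of the primary and secondary endpoints are unaffected. This is a minor correction, worth making because it is cheap and removes an outcome-dependent route out of the per-protocol populations.

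**What to change.** In SAP 6.2.2, assign the end date by group, following 4.8.2:

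- Subjects with recurrence, other cancer or death: count zero-compliance days from D_LCV/V4 to dfs_event_date.
- Subjects leaving without an event: count from D_LCV/V4 to 3 years from randomization.
- Both groups: add days on non-allowed breaks, as now.

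Drop E_endofstudydtm as an end date for this count. It can stay among the possible values of D_LCV/V4. Settle this before population membership is assigned and the blind is broken. The cost is about one sentence in the SAP and one line of code, with no new data.

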6.3 Subject disposition

A skeleton CONSORT flowchart is shown in Figure 3. The layout of the flowchart may be updated in accordance with the guidelines of the selected journal(s).

[figure not shown]

Figure 3. Skeleton CONSORT flowchart

7 Safety interim analyses

7.1 Safety interim analysis 2018

Data was extracted from the eCRF on March 27th, 2018, including subjects that were randomized up to and including March 12th, 2018, with follow-up up to and including March 27th, 2018. The safety report was sent to the Safety Monitoring Committee (SMC) on April 13th, 2018. The frequency of serious adverse events (SAEs) and AEs per randomized arm, visit, and type of SAE (see Table 8 for categories) was presented. The frequency of AEs at the first visit and in all visits combined, in total and stratified by intensity (see Table 8 for categories), was compared between the randomized arms using Fisher's exact test. Information on all SAEs and AEs were listed, see Table 8 for details.

7.2 Safety interim analysis 2020

Data was extracted from the eCRF on January 17th, 2020, including subjects that were randomized up to and including October 21st, 2019, with follow-up up to and including January 17th, 2020. The safety report was sent to the SMC on March 5th, 2020.

The number of SAEs were summarized by randomized arm and visit. Fisher's exact test was used to test differences in frequencies of SAEs between randomized arms for each visit. Information on all SAEs were listed, see Table 8 for details. Similarly, the total number of AEs, and number of AEs per AE type (using the categories listed under "Type of SAE" in Table 8), were summarized by randomized arm and visit, and compared between arms for each visit using Fisher's exact test. The number of subjects with multiple AEs was also summarized by randomized arm, visit, and type of AE.

Table 8. SAE and AE details included in the 2018 and 2020 safety reports to the SMC

SAE variable	Categories
Visit number	4-9 (2018 report), 4-15 (2020 report)
SAE day	Day in relation to randomization date
Randomized arm	0/1 (not disclosing associated treatment)
Type of SAE	 Hematological
	 Cancer
	 Cardiovascular
	 CNS/Neurological
	 Dermatological
	- Endocrine
	 Eyes, ears, nose, throat
	 Gastrointestinal
	Urogenital
	Hormonal
	Immunological
	 Musculoskeletal
	Respiratory
	– Other
SAE description	 Leads to death
	 Is life threatening
	Other important medical event
	 Requires hospitalization for more than 24
	hours or extended medical care
	Causes permanent or significant
	invalidity/functional impairment
Intensity	– Mild
	- Moderate
T (185)	- Severe
Treatment modification	- Unchanged
	- Stopped
B "	Other, e.g., treatment pause
Result	- Restored
	- Under improvement
	Not Restored, with sequels
	Death

8 Analysis of trial endpoints

All tests and confidence intervals (CIs) will be two-sided. The significance level will be 5 %, and CIs will have 95 % confidence level. The endpoints and their respective variables and populations are summarized in Table 9.

Table 9. Specification of variables and populations for the primary endpoint or secondary endpoints 1-5 in the ALASCCA trial. Mutation A: PIK3CA exon 9 and 20 hotspot small mutations, Mutation B: other PIK3CA, PIK3R1 and PTEN non-silent small mutations and focal/homozygous deletion of PTEN.

Endpoint	Specification	Time variable	Event indicator	Population	Subgroup
Primary endpoint	TTR assessed at 3 years between randomized arms	ttr3y	rec_status_3y	FAP	Mutation A
Secondary endpoint 1	DFS assessed at 3 years between randomized arms	dfs3y	dfs_status_3y	FAP	Mutation A
Secondary endpoint 2	TTR assessed at 3 years between randomized arms	ttr3y	rec_status_3y	FAP	Mutation B
Secondary endpoint 3	DFS assessed at 3 years between randomized arms	dfs3y	dfs_status_3y	FAP	Mutation B
Secondary endpoint 4	OS assessed at 5 years between randomized arms	os5y	os_status_5y	FAP	Mutation A
Secondary endpoint 5	OS assessed at 5 years between randomized arms	os5y	os_status_5y	FAP	Mutation B

8.1 Primary efficacy analysis

The analysis of the primary endpoint TTR assessed at 3 years from randomization in subjects with somatic alterations in the PIK3CA gene (exons 9/20) will be performed on a subset of the FAP containing only subjects with such somatic alterations.

The primary efficacy analysis will consist of a Cox proportional hazards model (PHM), including the covariate *Treatment* (ASA vs Placebo, defined by randomization). The baseline hazard will be stratified by the covariates used in the randomization – location (colon/rectum), and stage (I/II/III, included as a categorical variable). The strata will thus be the following

- Stratum 1: Colon, Stage II
- Stratum 2: Colon, Stage III,
- Stratum 3: Rectum, Stage I,
- Stratum 4: Rectum, Stage II,
- Stratum 5: Rectum, Stage III.

The Breslow method will be used to handle tied event-times. The model is given by

$$h_i(t) = h_{0,i}(t) \cdot \exp(\beta_{Treat} \cdot Arm),$$

where $h_j(t)$ and $h_{0,j}(t)$ denote the hazard function and baseline hazard function, respectively, for stratum j, j=1,...,5, and Arm denotes randomized arm (ASA=1, Placebo=0).

A HR=exp(β_{Treat}) comparing the hazard rates of the ASA and placebo arms will be estimated, along with a two-sided 95 % CI, and a two-sided p-value for testing the null hypothesis

 H_0 : $\beta_{Treat} = 0$

against the alternative hypothesis

 H_1 : $\beta_{Treat} \neq 0$.

The proportional hazards assumption (PHA) of the Treatment variable will be assessed using the Grambsch-Therneau test with a significance level of 5 %. If the PHA is violated, the overall HR will still be reported as the primary efficacy estimate, but an additional analysis will be added where follow-up is divided into two intervals, 0-1.5 years, and 1.5-3 years from randomization, and one HR for Treatment will be estimated for each time interval by adding an interaction term between Treatment and the time intervals.

In addition to the Cox PHM, TTR in the two treatment arms (ASA and Placebo) will be visually inspected by the cumulative incidence function (CIF) using Aalen-Johansen estimates, including 95% CIs, from time of randomization until three years of follow-up. Death will be considered a competing event. The 1- and 3-year Aalen-Johansen estimates of cumulative incidence of CRC recurrence in each arm, along with 95 % CIs, will also be presented. Kaplan-Meier (KM) curves estimating the net proportion of CRC recurrence, including 95% CIs, from time of randomization until three years of follow-up will be included as a supplementary figure.

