4.5.2 Updated calculation in protocol version 5.2

An updated sample size calculation was included in the ALASCCA Clinical Study Protocol Version 5.2 after 3206 patients had been screened. The three-year cumulative incidence of recurrence in the placebo arm was estimated to 18 % based on the Stage/Risk factor-specific estimates in Osterman and Glimelius (2018)^[1], and a 10 % drop-out rate was assumed. A total of 150 subjects in each arm would have to be included to detect a risk ratio (RR) of 0.38 for comparison between the ASA and placebo arms with 80 % power and a two-sided alpha of 0.05. Assuming 15 % of screened patients have somatic alterations in the PIK3CA (exon 9 and/or 20) gene, a total of 3750 patients will have to be screened. The estimate of a 15 % mutation rate was based on the 3206 first screened patients. The sample size calculation was based on a two-sample test for proportions. Details of the initial sample size calculation are listed in Table 2.

Table 2. Details of the updated sample size calculation in protocol version 5.2.

Power (%)	80
Two-sided alpha (%)	5
Minimal follow-up (months)	36
Mutation rate (%)	15
3-year cumulative incidence of recurrence in the placebo arm (%)	18
RR	0.38
Number of subjects in each arm (incl. 10 % drop-out)	150
Number of subjects in each arm (excl. 10 % drop-out)	135
Number of patients needed to be screened	3750

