Specification	Time variable(s)	Event indicator(s)	Population	Subgroup
TTR between randomized arms	ttr3y	rec_status_3y	PP3	Mutation A
TTR between randomized arms	ttr3y	rec_status_3y	PP3	Mutation B
TTR and DFS between randomized arms	ttr3y, dfs3y	rec_status_3y, dfs_status_3y	FAP	Mutation A + Mutation B
TTR and DFS between randomized arms	ttr3y, dfs3y	rec_status_3y, dfs_status_3y	FAP	Clonal high- confidence drivers: Mutation A + Mutation B
TTR between randomized arms	ttr3y	rec_status_3y	FAP	Active treatment Mutation A vs Placebo Mutation A + Mutation B
TTR starting 6 months from randomization	ttr3y	rec_status_3y	FAP	Mutation A
TTR starting 6 months from randomization	ttr3y	rec_status_3y	FAP	Mutation B
TTR and DFS between randomized arms	ttr3y, dfs3y	rec_status_3y, dfs_status_3y	FAP	Mutation A, colon cancer
TTR and DFS between randomized arms	ttr3y, dfs3y	rec_status_3y, dfs_status_3y	FAP	Mutation A, rectal cancer
TTR and DFS between randomized arms	ttr3y, dfs3y	rec_status_3y, dfs_status_3y	FAP	Mutation A, left- sided colon cancer
TTR and DFS between randomized arms	ttr3y, dfs3y	rec_status_3y, dfs_status_3y	FAP	Mutation A, right- sided colon cancer
TTR and DFS between randomized arms	ttr3y, dfs3y	rec_status_3y, dfs_status_3y	FAP	Mutation A, neoadjuvant and/or adjuvant treatment received

Specification	Time variable(s)	Event indicator(s)	Population	Subgroup
TTR and DFS between randomized arms	ttr3y, dfs3y	rec_status_3y, dfs_status_3y	FAP	Mutation A, neoadjuvant and/or adjuvant treatment not received
TTR and DFS between randomized arms	ttr3y, dfs3y	rec_status_3y, dfs_status_3y	FAP	Mutation A, rectal cancer, any neoadjuvant treatment received
TTR and DFS between randomized arms	ttr3y, dfs3y	rec_status_3y, dfs_status_3y	FAP	Mutation A, rectal cancer, no neoadjuvant treatment received
TTR and DFS between randomized arms	ttr3y, dfs3y	rec_status_3y, dfs_status_3y	FAP	Mutation A, MSI-H
TTR and DFS between randomized arms	ttr3y, dfs3y	rec_status_3y, dfs_status_3y	FAP	Mutation A, MSS/MSI-L
TTR and DFS between randomized arms	ttr3y, dfs3y	rec_status_3y, dfs_status_3y	FAP	Mutation B, colon cancer
TTR and DFS between randomized arms	ttr3y, dfs3y	rec_status_3y, dfs_status_3y	FAP	Mutation B, rectal cancer
TTR and DFS between randomized arms	ttr3y, dfs3y	rec_status_3y, dfs_status_3y	FAP	Mutation B, left- sided colon cancer
TTR and DFS between randomized arms	ttr3y, dfs3y	rec_status_3y, dfs_status_3y	FAP	Mutation B, right- sided colon cancer

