The statistical software R (R Foundation for Statistical Computing) will be used, in a version released less than a year before the time of analysis of the primary and secondary endpoints.

10 Listing of tables and figures

Note that the table and figure numbering in the below sections does not necessarily reflect the actual numbering in future publications. Some of the tables and figures may be published separately and in different order. Table formatting, e.g. number of decimals/significant digits, headings, row ordering etc. may be changed to follow the specifications of the selected journal(s).

Table 12. List of tables.

Table	Description	Population	Columns
Table 1.	Patient characteristics for randomized subjects in the ALASCCA trial.	FAP	Randomized to ASA Randomized to Placebo
Table 2.	Results from analysis of primary endpoint, and secondary endpoint 1-3. If the PHA is violated, one HR per time-interval (in addition to the overall HR).	FAP	N per randomized arm, no. of events per randomized arm, HR, 95% CI, p-value
Table 3.	Results from analysis of secondary endpoints 4-5.	FAP	N per randomized arm, no. of events per randomized arm, HR, 95% CI, p-value
Table 4.	Results from analyses of exploratory endpoints.	FAP/PP3	N per randomized arm, no. of events per randomized arm, HR, 95% CI
Table 5.	SAEs per randomized arm.	SP	Number of SAEs per randomized arm
Table 6.	AEs per randomized arm.	SP	Number of AEs per randomized arm
Supplementary Table 1.	Number of AEs per randomized arm and visit, stratified by type of AE.	SP	Number of AEs per randomized arm

Table 13. List of figures. Mutation A: Mutation in PIK3CA exons 9/20, Mutation B: Mutation in PIK3CA (other exons), PIK3R1, PTEN.

Figure	Description	Population	Axis labels (if applicable)
Figure 1.	CONSORT flowchart showing number of screened patients, exclusions, randomized subjects.		
Figure 2a.	CIF curves, with 95% CIs, comparing TTR assessed at 3 years between ASA and Placebo in subjects with somatic alterations in PIK3CA (exons 9/20).	FAP, Mutation A	X-axis "Months from randomization" Y-axis "Cumulative incidence of CRC recurrence (%)"
Figure 2b.	CIF curves, with 95% CIs, comparing TTR assessed at 3 years between ASA and Placebo in subjects with somatic alterations in PIK3CA (other exons), PIK3R1, or PTEN.	FAP, Mutation B	X-axis "Months from randomization" Y-axis "Cumulative incidence of CRC recurrence (%)"

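### Early and late hazard ratios are reported only if an underpowered proportional-hazards test is significant, so the timing of the aspirin effect would be reported selectively

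*SAP*

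**What the plan says.** SAP 8.1 fits a Cox model stratified by location and stage and reports one overall HR for ASA against placebo. It then sets a check: "The proportional hazards assumption (PHA) of the Treatment variable will be assessed using the Grambsch-Therneau test with a significance level of 5" per cent. The time scale of the test is not stated.

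If the check rejects, "an additional analysis will be added where follow-up is divided into two intervals, 0-1.5 years, and 1.5-3 years from randomization", with one HR for each. If it does not, no interval HR is produced. The condition is repeated in SAP section 10, where Table 12 describes the main results table: "If the PHA is violated, one HR per time-interval (in addition to the overall HR"). The Table 15 template carries the same condition.

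SAP 8.2.1 applies the 8.1 method to secondary endpoints 1-5. The two intervals stop at 3 years, so no split is defined for OS at 5 years (endpoints 4 and 5).

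Whatever the test shows, 8.1 also presents cumulative incidence curves with 95% CIs, the 1- and 3-year Aalen-Johansen estimates for each arm, and supplementary Kaplan-Meier curves. The only between-arm measure in the results templates is the HR.

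**The concern.** The rule lets a significance test decide whether the reader sees an estimate. If the test has little power, two things follow. A real early/late difference will usually go unreported as an HR contrast. When the contrast is reported, it has been selected for being large and so overstates the truth.

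A changing effect is plausible here. SAP 4.1 and 4.8.2 allow some subjects on adjuvant chemotherapy to start study drug only after chemotherapy ends. Table 10 also lists "TTR starting 6 months from randomization" as an exploratory analysis, although 8.3 makes that list optional and gives no reason for the entry.

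What is at stake is the published account of when ASA acts, not whether it acts.

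**Working it through.** **1. Reproduce the design.** Inputs from SAP 4.5.2: placebo 3-year recurrence 18%, risk ratio 0.38 (so 0.18 x 0.38 = 6.84% on ASA), "with 80 % power and a two-sided alpha of 0.05", two-sample test for proportions, 10% drop-out. The pooled formula is n = [1.96 sqrt(2 p(1-p)) + 0.8416 sqrt(p1(1-p1) + p2(1-p2))]^2 / (p1-p2)^2. With p1 = 0.18, p2 = 0.0684 and p = 0.1242 it gives 136 per arm, and 136/0.90 = 152. The plan states 135 and 150, so its figure is reproduced to within 2 patients.

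**2. Events.** The documents give no event count. At the design effect: 135 x 0.18 + 135 x 0.0684 = 24.3 + 9.2 = 33.5. With a weaker effect (assumed risk ratio 0.70) and all 150 per arm: 27 + 18.9 = 45.9.

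**3. Closed-form power of the test.** Let D events split evenly between the intervals, with ASA share q. The SE of the late/early log HR contrast is sqrt(2 / ((D/2) q(1-q))). A test for linear trend against a step change has relative efficiency of about 0.866.
- D = 40, q = 0.38: SE = sqrt(2/(20 x 0.2356)) = 0.65. Then ln 3/0.65 x 0.866 = 1.46, and power is about 31%.
- D from 35 to 45 and q from 0.25 to 0.5: power 23% to 36%, so a threefold change is missed in 64-77%.
- Events needed for 80% power: 4 x (2.802/(0.866 ln 3))^2 / (q(1-q)) = 139 (q = 0.5), 147 (q = 0.38), 165 (q = 0.30).

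**4. Simulated power.** Stratified Cox model, score form of the Grambsch-Therneau test at 5%, censoring at 3 years plus 21 days, Kaplan-Meier-transformed time unless noted.

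| Scenario (assumed) | Missed |
|---|---|
| Threefold change at 1.5 years, constant baseline hazard, 35-45 events | 69-80% |
| Same, front-loaded baseline hazard | 71-83% |
| Same, 60% of recurrences found at the 1- or 3-year scan | 82-83% |
| Same, log time scale | 76-88% |
| HR 1.0, then 0.35 from 1.5 years | 75% |
| HR 0.35, then 1.0 from 1.5 years | 72% |
| HR 1.0, then 0.35 from 6 months | 82% |
| HR 1.0, then 0.2 from 1.5 years | 59% |

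Under a constant HR of 0.35 or 0.5 the test rejects in about 5%, as it should.

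The HR 1.0/0.35/0.2 rows used 150 per arm, 10% drop-out and stratum shares of 0.33, 0.30, 0.10, 0.12 and 0.15 with relative hazards 0.55, 1.6, 0.4, 0.8 and 1.6. None of the stratum figures is in the documents.

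**5. What is reported when the test fires.** In closed form at D = 40 and q = 0.38, a step contrast must reach exp(1.96 x 0.65) = 3.6-fold to be significant, which already exceeds a true 3-fold. In simulation the median contrast on firing is about 6- to 7-fold at 40-45 events and up to 9-fold at 35, and it exceeds the truth in 91-96% of firings. Under a constant HR the median on firing is about 5- to 6-fold, where the truth is 1.

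**6. What is reported without the gate.** Over all trials with a constant baseline hazard, the median contrast is about 3.1- to 3.3-fold against a true 3-fold. With scan clustering it is somewhat low, at 2.3 to 2.8.

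**7. Precision without the gate.** At 40 events and q of 0.30-0.38, each interval HR has a 95% CI factor of 2.5-2.6, and the late/early ratio 3.6-3.9. At the design's 33.5 events, split evenly (4.6 and 12.15 per interval): exp(1.96 x sqrt(1/4.6 + 1/12.15)) = 2.9 per interval, and about 4.6 for the ratio.

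**The case against.** Three stronger readings are tempting, and the documents support none of them.

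- *The SAP takes a non-significant test as proof of a constant effect.* It says no such thing; it only decides whether two supplementary HRs are added.
- *The primary result is at risk.* It is not. Even on rejection, "the overall HR will still be reported as the primary efficacy estimate", and its CI, p-value and alpha do not depend on the check.
- *The reader is left with nothing on timing.* Curves and 1- and 3-year incidences by arm always appear, so a late separation would be visible. What is missing is an ungated early-versus-late comparison between arms.

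Nor does the 6-month analysis in Table 10 show that the sponsor expects a delay. No reason is given, and delayed starts after chemotherapy are another explanation.

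The strongest objection is to the remedy. With intervals as wide as in step 7, a true threefold change would usually not be distinguishable from none. That stands: the fix does not answer the timing question. It does remove a bias that the rule itself creates, because a wide interval reported every time is honest and one shown only when extreme is not.

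It is also fair that the miss rates rest on assumed hazards. Most of the variants tried make the test look worse. The most favourable threefold case still missed 64%.

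The missing between-arm 3-year contrast is a separable point. It belongs here because it needs no proportional-hazards assumption and is the quantity on which the trial was sized.

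**Conclusion.** The concern holds as one of selective reporting. At about 33 to 45 events, the test that controls the interval HRs misses a threefold change at 1.5 years in about 70-80% of trials, and in somewhat more if recurrences cluster at the scheduled scans. When it fires, the contrast is inflated about twofold. In about 5% of trials with a constant HR it produces a spurious contrast of about 5- to 6-fold.

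These figures rest on assumed early and late HRs, baseline hazard shape, stratum mix and share of scan-detected recurrences. The direction held in every variant tried. The consequence is for interpreting when the effect occurs; the validity of the primary analysis is untouched. The change is worth making because it is cheap.

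**What to change.** In SAP 8.1:
- Keep the overall stratified HR as the primary estimate and test.
- Remove the significance trigger. For the primary endpoint and secondary endpoints 1-3, always report the 0-1.5 and 1.5-3 year HRs with 95% CIs and no p-values.
- For OS at 5 years (secondary endpoints 4-5), define intervals that cover the full 5 years and report them in the same way.
- Give the Grambsch-Therneau p-value as descriptive only, and state that p > 0.05 does not show proportionality.
- Add the between-arm difference or ratio in 3-year cumulative incidence with a 95% CI, from the Aalen-Johansen estimates for TTR and the Kaplan-Meier estimates for DFS.
- Amend the conditional wording in Tables 12 and 15 to match.

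The cost is SAP wording and a few table rows from models and estimates already planned, with no new data, patients or alpha. The downside is imprecision: each interval HR will have a 95% CI of roughly the estimate multiplied or divided by 2.5 to 2.9, and the report should say so.
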